7.8 Safety Analyses

Subject safety is assessed by AEs, labs, vital signs, 12-lead ECGs, and findings from the physical examinations. The occurrence of neurological side effects will be assessed by looking at any worsening in scores for each of the Simpson-Angus scale, Barnes Akathisia scale, and AIMS. Suicidal ideation and suicidal behavior will be measured by C-SSRS. All summaries related to safety analyses will use the safety population and will be presented by treatment groups.

7.8.1 Adverse Events

AEs will be summarized using subject incidence table by treatment period (titration, maintenance, combined titration and maintenance, and tapering). An overview of TEAE will be presented. This table will include numbers and percentages of subjects experiencing at least 1 TEAE, study drug-related TEAE, AE leading to study drug discontinuation, severe TEAE, serious TEAE, related TESAE, AESI, and TEAE with outcome of death (Table 14.3.1.1).

Additionally, the number and percent (%) are calculated based on the number of unique subjects within each category (e.g., preferred term) by treatment group. A subject reporting multiple events of the same category will be counted only once for that category. For summary purpose, AE relationship to the study drug will be grouped into “Unrelated” for “unrelated” or “unlikely related” and “Related” for “possibly”, “probably”, or “definitely related”. For subjects with more than one event coded to the same PT, the subjects will be counted for the categories with the strongest relationship and the greatest severity. The following subject incidence tables will be presented.

- TEAEs by PT (Preferred Term) sorted by the decreasing order of subject incidence in the combined active dose group (Table 14.3.1.2.1 – Table 14.3.1.2.3)
- TEAEs by SOC (System Organ Class) and PT sorted alphabetically (Table 14.3.1.3.1 – Table 14.3.1.3.3)
- Study Drug-Related TEAEs by SOC and PT (Table 14.3.1.4.1 – Table 14.3.1.4.3)
- Severity of TEAEs by SOC and PT (Table 14.3.1.5.1 – Table 14.3.1.5.3)
- TESAEs by SOC and PT when applicable (Table 14.3.1.6)

- Number and percent of patients reporting common AEs ($\geq 5\%$ in any group) by PT (Table 14.3.1.7.1 – Table 14.3.1.7.3)
- TEAEs leading to study drug discontinuation by SOC and PT (Table 14.3.1.8)
- Treatment Emergent AESI by SOC and PT (Table 14.3.1.9)

Where warranted by the subject incidence, these same tables may be presented by treatment period (Titration, Maintenance and Conversion/Tapering).

A subject data listing will be provided for all adverse events (Listing 16.2.3.1.1). Included in the listing are the reported term, PT, SOC, TEAE flag, study day when AE starts, duration, relationship, severity, action taken, outcome, and seriousness category.

Data listings will be provided for subjects who die on study, experience SAEs, have TEAEs leading to study drug discontinuation, or AEs of special interest (Listing 16.2.3.1.2 – Listing 16.2.3.1.5).

7.8.2 *Laboratory Test*

Clinical laboratory values will be summarized by treatment group and visit using descriptive statistics for hematology, biochemistry, and urinalysis. For quantitative laboratory parameters, both actual values and change from baseline values will be summarized (Table 14.3.2.1, Table 14.3.3.1, and Table 14.3.4.1).

Laboratory test result will be assigned a low, normal, high (LNH) classification according to whether the value is below (L), within (N), or above (H) the reference range provided by the laboratory. Within-treatment comparisons will be based on three by three tables (shift tables), that, for a particular laboratory test, compare the LNH classification at baseline to the LNH classification at visit. By subject-listings of all laboratory values will be provided for subjects who have L or H classification in any of their laboratory tests (Table 14.3.2.2, Table 14.3.3.2, and Table 14.3.4.2).

Note the summary and shift tables will only use the planned/scheduled tests. However, both scheduled and repeat tests will be in the data listing.

A complete lab data listing, including hematology, biochemistry, and urinalysis will be provided for all subjects. Investigator assessment of clinical significance is based on the local laboratory reference ranges (Listing 16.2.3.2.1 – Listing 16.2.3.2.3).

7.8.3 *Vital Signs, Height, Weight, and BMI*

Vital signs (body temperature, heart rate, respiration rate, systolic blood pressure, and diastolic blood pressure), and their changes from baseline will be summarized by treatment group and

visit (Table 14.3.5, Listing 16.2.3.3). Subject body size (weight, height, and BMI) will be summarized similarly (Table 14.3.6, Listing 16.2.3.4).

7.8.4 12-Lead ECG

By-visit tabular summaries of the quantitative ECG parameters and the overall ECG findings (normal, abnormal not clinically significant, or abnormal clinically significant) will be presented. The QT interval will be corrected using Fridericia's method.

ECG results will be summarized by visit by treatment group using descriptive statistics (for quantitative ECG parameters) and frequency tables (for qualitative ECG parameters, including the overall ECG finding). For quantitative ECG parameters, both actual values and change from screening values will be summarized (Table 14.3.7.1 and Table 14.3.7.2).

Data listings will be presented for ECG parameters by visit. QTcF meeting the criteria of >450 but ≤480, >480 but ≤500 or >500 msec for the absolute value, or >30 msec or >60 msec increase from baseline will be identified (Listing 16.2.3.5.1 and Listing 16.2.3.5.2).

7.8.5 *Columbia Suicide Severity Rating Scale (C-SSRS)*

C-SSRS outcomes will be summarized using number and percent of subjects by categories for suicidal ideation only, suicidal behavior only and suicidality (ideation and behavior combined). The summary will be presented by treatment groups. The proportion of subjects in each treatment group will be compared with the proportion of subjects in the placebo group using the Fisher's exact test (Table 14.3.8 and Listing 16.2.3.6).

7.8.6 *Infrequent Behaviors Checklist*

Infrequent behaviors will be listed for each subject by treatment group (Listing 16.2.3.7).

7.8.7 *Other Special Tests*

The occurrence of neurological side effects will be assessed by looking at the changes in scores from baseline to post-baseline visits for each of the Simpson-Angus scale (Listing 16.2.3.8), Barnes Akathisia scale (Listing 16.2.3.9), and AIMS (Listing 16.2.3.10). For each item on each of these scales, the number (and percentage) of subjects with a worse score at any post-baseline visit, compared to baseline, will be presented. A listing of these subjects will also be provided.

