6.14.1 Adverse Events

AEs will be classified into standardized medical terminology from the verbatim description (Investigator term) using the Medical Dictionary for Regulatory Activities (MedDRA). AEs will be summarized using discrete summaries at the subject and event level by system organ class and preferred term for each treatment group. Similarly, treatment-emergent AEs will be summarized by severity and relationship separately. Verbatim description and all MedDRA level terms, including the lower level terms, for all AEs will be contained in the subject data listings.

All AEs occurring after randomization and throughout the study period will be recorded. For subjects who receive SM, treatment-emergent AEs (TEAEs) will be collected starting after the first dose of SM (Visit 3) to the end of the study. These AEs include those that emerge during treatment or worsen in severity during treatment. These AEs will be tabulated, listed and analyzed.

Separate TEAE incidence tables will be presented for the three treatment groups. The incidence rates for all SADRs will also be summarized as described for all TEAEs.

In addition, these same tables will be presented by treatment period (Titration, Maintenance, and combined Titration and Maintenance). For the combined Titration and Maintenance Periods, the incidence of TEAEs will also be presented by highest severity reported and the dose of SM at first occurrence.

Listings (and tabular summaries, if warranted) of deaths, other SAEs, and other significant TEAEs, including TEAEs resulting in treatment discontinuation, will be provided.

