| 14.2.6.1 | Parenting Stress Index – Short Form (PSI-4-SF) Total Score, Change from Baseline to Visit 6 | ITT Population |
| 14.2.6.2 | Parenting Stress Index – Short Form (PSI-4-SF) Parental Distress Subscale Scores, Change from Baseline to Visit 6 | ITT Population |
| 14.2.6.3 | Parenting Stress Index – Short Form (PSI-4-SF) Parent-Child Dysfunctional Interaction Subscale Scores, Change from Baseline to Visit 6 | ITT Population |
| 14.2.6.4 | Parenting Stress Index – Short Form (PSI-4-SF) Difficult Child Subscale Scores, Change from Baseline to Visit 6 | ITT Population |
| 14.2.7.1 | SNAP-IV ADHD Inattention Subscale Score and Change from Baseline to Visit 6 | ITT Population |
| 14.2.7.2 | SNAP-IV ADHD Hyperactivity/Impulsivity Subscale Score and Change from Baseline to Visit 6 | ITT Population |
| 14.2.7.3 | SNAP-IV ADHD oppositional defiant disorder Score and Change from Baseline to Visit 6 | ITT Population |
| 14.2.7.4 | SNAP-IV ADHD Combined Scale Rating Score and Change from Baseline to Visit 6 | ITT Population |
| 14.2.8.1a | Subgroup Analysis of Investigator Clinical Global Impression – Improvement (CGI-I) Score by Visit (Age) | ITT Population |
| 14.2.8.1b | Subgroup Analysis of Investigator Clinical Global Impression – Improvement (CGI-I) Score by Visit (Gender) | ITT Population |

| | | |
|------------|---|-------------------|
| 14.2.8.1c | Subgroup Analysis of Investigator Clinical Global Impression – Improvement (CGI-I) Score by Visit (Race) | ITT Population |
| 14.2.8.2a | Subgroup Analysis of Caregiver Clinical Global Impression – Improvement (CGI-I) Score by Visit (Age) | ITT Population |
| 14.2.8.2b | Subgroup Analysis of Caregiver Clinical Global Impression – Improvement (CGI-I) Score by Visit (Gender) | ITT Population |
| 14.2.8.2c | Subgroup Analysis of Caregiver Clinical Global Impression – Improvement (CGI-I) Score by Visit (Race) | ITT Population |
| 14.3.1.1 | Overall Incidence of Treatment-Emergent Adverse Events by Study Period | Safety Population |
| 14.3.1.2.1 | Incidence of Treatment-Emergent Adverse Events by Preferred Term – Titration and Maintenance Period | Safety Population |
| 14.3.1.2.2 | Incidence of Treatment-Emergent Adverse Events by Preferred Term – Titration Period | Safety Population |
| 14.3.1.2.3 | Incidence of Treatment-Emergent Adverse Events by Preferred Term – Maintenance Period | Safety Population |

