| 14.3.1.8.3 | TEAEs leading to study drug discontinuation by SOC and Preferred Term – Maintenance Period | Safety Population |
| 14.3.1.9.1 | Treatment Emergent AESI by SOC and Preferred Term – Titration and Maintenance Period | Safety Population |
| 14.3.1.9.2 | Treatment Emergent AESI by SOC and Preferred Term – Titration Period | Safety Population |
| 14.3.1.9.3 | Treatment Emergent AESI by SOC and Preferred Term – Maintenance Period | Safety Population |
| 14.3.2.1 | Hematology: Change from Baseline by Visit | Safety Population |
| 14.3.2.2 | Hematology: Shift from Baseline Classification by Visit | Safety Population |
| 14.3.3.1 | Blood Chemistry: Change from Baseline by Visit | Safety Population |
| 14.3.3.2 | Blood Chemistry: Shift from Baseline Classification by Visit | Safety Population |
| 14.3.4.1 | Urinalysis: Change from Baseline by Visit | Safety Population |

| | | |
|----------|---|-------------------|
| 14.3.4.2 | Urinalysis: Shift from Baseline Classification by Visit | Safety Population |
| 14.3.5 | Vital Signs: Change from Baseline at End of Study | Safety Population |
| 14.3.6 | Subject Body Size: Change from Baseline by Visit | Safety Population |
| 14.3.7.1 | 12-Lead ECG Intervals: Change from Baseline by Visit | Safety Population |
| 14.3.7.2 | 12-Lead ECG Overall Findings: Shift from Baseline Classification by Visit | Safety Population |
| 14.3.8 | Columbia Suicidal Severity Rating Scale by Visit | Safety Population |

| Listing No. | Title | Population |
|--------------------|---|-----------------------|
| 16.1.7 | Subject Randomization Schedule | Randomized Population |
| 16.2.1.1 | Subject Disposition and Reason for Disposition | Randomized Population |
| 16.2.1.2 | Subjects Who had Major Protocol Deviations | Randomized Population |
| 16.2.1.3 | Subjects Inclusion and the Reason for Exclusion from Analysis Populations | Randomized Population |
| 16.2.1.4 | Demographics and Baseline Characteristics | Randomized Population |
| 16.2.1.5 | Medical History | Randomized Population |
| 16.2.1.6 | R-MOAS Scale at Baseline | Randomized Population |
| 16.2.1.7 | Viteillo Aggression Scale at Baseline | Randomized Population |
| 16.2.1.8 | Study Drug Accountability and Compliance | |
| 16.2.1.9.1 | Prior Medications | Randomized Population |
| 16.2.1.9.2 | Concomitant Medications | Randomized Population |
| 16.2.1.9.3 | Prohibited Medications | Randomized Population |

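### SAP 7.8.1 promises adverse event summaries for the taper period, but Appendix 2 has no by-term table for non-serious events or AESIs that start in the conversion/taper week

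*SAP*

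**What the plan says.** SAP 7.8.1 contains two statements that do not match. The first is firm and names the taper period: "AEs will be summarized using subject incidence table by treatment period (titration, maintenance, combined titration and maintenance, and tapering". The second, after the list of tables, is permissive: "Where warranted by the subject incidence, these same tables may be presented by treatment period (Titration, Maintenance and Conversion/Tapering".

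The same section gives the discontinuation table (14.3.1.8) and the AESI table (14.3.1.9) as single tables with no period limit. In Appendix 2 each becomes three tables. The first of the AESI set is titled "Treatment Emergent AESI by SOC and Preferred Term – Titration and Maintenance Period"; the other two cover titration alone and maintenance alone. The preferred-term set follows the same pattern, beginning with "Incidence of Treatment-Emergent Adverse Events by Preferred Term – Titration and Maintenance Period".

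Two adverse event tables are not tied to one of those three periods:

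- Table 14.3.1.1, the overview, titled "Overall Incidence of Treatment-Emergent Adverse Events by Study Period" in Appendix 2. According to 7.8.1 its rows include "serious TEAE, related TESAE, AESI, and TEAE with outcome of death (Table 14.3.1.1").
- Table 14.3.1.6, serious treatment-emergent events by SOC and preferred term.

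SAP 7.8 adds: "All summaries related to safety analyses will use the safety population and will be presented by treatment groups".

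Protocol 6.14.1 sets the collection window. For subjects who receive study medication, TEAEs "will be collected starting after the first dose of SM (Visit 3) to the end of the study". It plans incidence tables for the three arms and then, additionally, the same tables by period. Its period list is titration, maintenance and the two combined.

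**The concern.** Dose reduction is not permitted in the study (Protocol 4.3.6), so for a child who completes Visit 6 the following week is the planned point of dose change. Under Protocol 3.2.3 the child is either tapered off or converted towards the open-label dose. Protocol 5.4.2.2 makes extrapyramidal symptoms, including akathisia, dystonia and tardive dyskinesia, events for special reporting.

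If the Appendix 2 list is what gets programmed, non-serious events with onset in that week drop out of every table that names the event. A by-arm AESI count would remain, but it cannot separate akathisia from dyskinesia. The only route back into a by-term table is the discretionary sentence. Because it has no threshold, the decision could be taken after the incidence is known. The SAP supersedes the protocol's statistical methods (SAP 1), so the protocol text does not restore what the table list leaves out.

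**Working it through.** No sample size, power or alpha figure is involved. The check is a count of tables and a comparison of texts.

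**Step 1: count the adverse event tables in Appendix 2 (14.3.1.1 to 14.3.1.9.3).**

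| Set | Content | Titration + maintenance | Titration | Maintenance | Conversion/taper |
|---|---|---|---|---|---|
| 14.3.1.2 | TEAE by PT | 1 | 1 | 1 | 0 |
| 14.3.1.3 | TEAE by SOC/PT | 1 | 1 | 1 | 0 |
| 14.3.1.4 | Relatedness | 1 | 1 | 1 | 0 |
| 14.3.1.5 | Severity | 1 | 1 | 1 | 0 |
| 14.3.1.7 | Common AEs by PT | 1 | 1 | 1 | 0 |
| 14.3.1.8 | Leading to discontinuation | 1 | 1 | 1 | 0 |
| 14.3.1.9 | AESI by SOC/PT | 1 | 1 | 1 | 0 |
| Total | | 7 | 7 | 7 | 0 |

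Seven sets of three give 21 tables. Adding 14.3.1.1 and 14.3.1.6 gives 23.

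**Step 2: follow one event.** Take a non-serious AESI with onset between Visit 6 and Visit 7.

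- It is a TEAE under Protocol 6.14.1, because the window runs to the end of the study.
- It is counted by arm in Table 14.3.1.1, if that table has a taper column. The table's title and the opening sentence of 7.8.1 together imply one.
- It is not in 14.3.1.6, because it is not serious.
- It is in none of the 21 period-specific tables.
- Its preferred term, SOC and start day appear in Listing 16.2.3.1.1. It also appears in the AESI listing, 16.2.3.1.5.

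**Step 3: compare with other outputs.** The disposition tables 14.1.3a to 14.1.3d do name tapering as a period. The gap is therefore specific to the by-term adverse event tables.

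**Step 4: look for an adverse event period rule.** SAP 4 defines the titration and maintenance periods for the daily IA diaries. The last-dose rule in SAP 6.4 concerns IA frequency. Neither assigns an adverse event to a period, so the SAP does not say where an event belongs if it starts after an early leaver's last dose.

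**Step 5: illustrate the size.** The inputs are the nominal durations in SAP 3.3.2: titration 14 days, maintenance 21, conversion/taper 7. For a completer the share of days in the last week is 7 / (14 + 21 + 7) = 7/42 = 16.7%. This equals the share of TEAEs only if the onset rate is constant, which the documents do not state. If the last-week rate were r times the earlier rate, the share would be 7r / (35 + 7r). As assumed values, r = 0.5 gives 3.5/38.5 = 9.1%, and r = 2 gives 14/49 = 28.6%.

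**The case against.** The strongest defence is that the SAP is not silent on this week. The overview table gives TEAE and AESI counts by arm and by study period. Serious events have a by-term table with no period limit. In 7.8.1 itself, the AESI and discontinuation tables carry no period limit either. Conversion/taper tables are allowed, and the listings hold the data to build them. All three EPS scales are given at Visit 7, and 7.8.7 plans the number of subjects worse at any post-baseline visit. The protocol's own list of periods also omits the taper week.

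Most of this stands, and it limits the point. A reader might infer that events in the last week cannot be compared by arm at all, or that there is no AESI table for it. The overview table rules out both readings. What the defence does not supply is a required table by term. The EPS-scale summary pools Visit 7 with earlier visits, and Appendix 2 gives it listings (16.2.3.8 to 16.2.3.10) but no numbered table.

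A second defence is that confining the main by-arm tables to the randomised fixed-dose period is reasonable. That is fair. The conversion kits move subjects towards the open-label dose, so a table by randomised arm through Visit 7 could credit conversion-week events to the wrong treatment. The contents of the conversion kit by arm cannot be checked, because the treatment schedule figure is not shown. This argues against making a whole-study table the main display. It does not argue against a separate table for the week.

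A reader might also infer that the protocol promised a whole-study by-term table which the SAP has removed. Protocol 6.14.1 mentions incidence tables by group before it adds the period versions, but it does not state that those base tables run to Visit 7.

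**Conclusion.** The concern holds as a conflict between SAP 7.8.1 and Appendix 2 that would leave the safety tables incomplete. No numbered by-term table covers non-serious TEAEs, or AESIs that are not serious, with onset in the conversion/taper week: zero of the 21 period-specific tables. Those events are still counted by arm in the overview and named in the listings.

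Three stronger conclusions are not supported:

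- **That early leavers' events after stopping are lost.** No adverse event period rule exists, so their assignment is undefined; the documents do not show that they are excluded.
- **That this week is the only time the drug is withdrawn.** Under Protocol 3.2.4, subjects can stop during titration without a taper kit, and those who stop in maintenance are offered one. Conversely, not everyone in the last week is being withdrawn, since those entering the extension are converted.
- **That about one TEAE in six would be missing from the by-term tables.** The 16.7% is a share of nominal days for a completer and becomes a share of events only under a constant onset rate. It illustrates scale and is not an estimate.

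The verdict rests on the text of 7.8.1 and the Appendix 2 titles. The table shells are not available, so the column layout of Table 14.3.1.1 is inferred. The primary efficacy analysis is not affected.

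**What to change.** Amend SAP 7.8.1 and Appendix 2 together, before unblinding:

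1. Replace the discretionary sentence with a required table of events with onset in the conversion/taper phase, at least for TEAEs by SOC and preferred term and for AESIs by SOC and preferred term. Present it by randomised arm, with separate columns for taper-kit and conversion-kit subjects, so that withdrawal and conversion are not mixed.
2. Make the numbering of Tables 14.3.1.8 and 14.3.1.9 agree between the body text and Appendix 2, and state the period each one covers.
3. Add a rule assigning adverse events to periods, including events that start after the last dose in subjects who leave early.
4. If a table from first dose to Visit 7 is wanted, label it supplementary and footnote that it includes conversion-week dosing.

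The cost is SAP wording and a few additional runs of existing table programs. Onset day, SOC and preferred term are already planned for the listing, so no new data are needed. The drawback is small counts, especially after the split by kit, so the tables should be read descriptively.

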8 VALIDATION

The Clinical Operations, Clinical Research, and Statistics groups at Supernus will work with [REDACTED] and [REDACTED] to ensure that the data collected for the study are of the highest quality possible. The

study monitor will be responsible for reviewing and verifying the accuracy of the data recorded on the electronic case report forms (eCRFs) direct from source documents at the investigative site. [REDACTED] will be responsible for performing edit checks and reviewing all data entered into the electronic database to identify discrepant and/or inconsistent values and to send queries to the clinical sites. The Investigator will be responsible for answering queries about discrepant data and providing electronic signatures to confirm data integrity.

The programming of Tables, Listings and Figures (TLFs) based on the clinical data is outsourced to [REDACTED]. Supernus seeks to ensure the quality of the reports provided by [REDACTED] in the form of TLFs must pass a rigorous validation process involving the following processes.

- Derived datasets must be independently reprogrammed by a second programmer. The separate datasets produced by the 2 programmers must match 100%.
- Tables must be independently reprogrammed by a second programmer for and the results from both programs must match.
- Figures must be checked for consistency against corresponding tables and listings, or independently reprogrammed if there are no corresponding tables or listings.
- Listings must be checked for consistency against corresponding tables, figures, and derived datasets.

The entire set of TLF must be checked for completeness and consistency prior to its delivery to Supernus.

The above validation process must be repeated any time TLFs are redelivered using different data. Execution of this validation process must be documented through the study Table of Programs that will be provided to Supernus at study conclusion.

